## 6 Study Assessments and Procedures

Before any study procedures are performed, all potential participants will be consented using an IRB/IEC-approved ICF. Additional procedural details related to the ICF, including educating participants on the symptoms and means of reporting suspected myocarditis or pericarditis, are provided in [Section 9.3](#). Study assessments will be performed in an outpatient setting at qualified study sites.

Refer to the SOE [Table 13-1](#) for the full list of visits and assessments. Due to the ongoing pandemic, safety follow-up may be completed via televisits, as permitted by country regulations.

### 6.1 Safety Assessments

Safety will be assessed through the collection and evaluation of solicited and unsolicited AEs ([Section 6.1.1.1.1](#)), MAAEs ([Section 6.1.1.1.1](#)), SAEs ([Section 6.1.1.1.2](#)), and AESIs ([Section 6.1.1.1.4](#)). Safety will also be assessed by physical examinations, vital sign measurements, and clinical safety laboratory assessments.

All suspected cases of COVID-19 in study participants will be diagnosed and clinically evaluated, which may require unscheduled study site visits and additional SARS-CoV-2 laboratory testing ([Section 6.1.2](#)). Participant COVID-19 diagnosis and clinical evaluation may be performed by an outside medical provider following local standard of care.

All suspected or confirmed cases of myocarditis or pericarditis will be diagnosed and clinically evaluated ([Section 6.1.3](#)).

Any abnormal laboratory test results or other safety assessments (eg, physical examinations, vital sign measurements), including those that worsen from baseline or are clinically significant in the medical and scientific judgment of the investigator, are to be recorded as AEs or SAEs as applicable.

## **6.1.1 Adverse Events**

### **6.1.1.1 Definitions**

#### **6.1.1.1.1 Adverse Events**

The investigator is responsible for reporting all AEs that are observed or reported during the study, regardless of their relationship to the IP or their clinical significance.

An AE is defined as any untoward medical occurrence in a participant enrolled into this study regardless of its causal relationship to the IP. Participants will be instructed to contact the investigator at any time after enrollment if any symptoms develop.

A solicited AE is defined as an AE that is recorded by participants in an eDiary from Day 1 through Day 7 in response to specific questions ([Section 6.1.1.5](#)). After study vaccination all participants will be instructed to record local and systemic solicited AE symptoms in an eDiary. Local solicited AEs will include injection site pain, redness, and swelling and lymphadenopathy (localized axillary, cervical or supraclavicular swelling or tenderness ipsilateral to the vaccination arm). Systemic solicited AEs will include fever, fatigue, headache, chills, myalgia, and arthralgia. Solicited local and systemic AEs will be used to assess reactogenicity and will be assigned a grade as described in [Section 6.1.1.2.1](#). Any such AEs starting more than 7 days after vaccination will be captured as unsolicited AEs.

An unsolicited AE is defined as any AE that is volunteered from the participant. Unsolicited AEs will be monitored for 28 days after vaccination.

An MAAE is defined as an AE that results in a visit to a medical professional (eg, telemedicine visits, physician's office visits, urgent care visits, emergency room visits, or hospitalization).

### **6.1.1.2      Serious Adverse Events**

An SAE is defined as any event that:

- Results in death
- Is immediately life-threatening
- Requires inpatient hospitalization or prolongation of existing hospitalization
- Results in persistent or significant disability/incapacity
- Is a congenital anomaly/birth defect
- Is an important medical event that may not result in death, be life-threatening, or require hospitalization but, based upon appropriate medical judgment, jeopardizes the participant or may require medical or surgical intervention to prevent one of the other outcomes listed in this definition. Examples of such medical events include allergic bronchospasm requiring intensive treatment in an emergency room or at home, blood dyscrasias or convulsions that do not result in inpatient hospitalization, or the development of drug dependency or drug abuse. All events of myocarditis and pericarditis will be considered important medical events and SAEs ([Section 6.1.3](#)).

### **6.1.1.3      Suspected Unexpected Serious Adverse Reactions**

A SUSAR is defined as a serious adverse reaction, the nature or severity of which is not consistent with the applicable product information (eg, IB for an unapproved IP).

### **6.1.1.4      Adverse Events of Special Interest**

An AESI (serious or nonserious) is defined as an AE or SAE of scientific and medical concern specific to the sponsor's product or program, for which ongoing monitoring and rapid communication by the investigator to the sponsor could be appropriate (ICH E2F; CIOMS VI).

For this study, prespecified AESIs will include the following events:

- Virologically confirmed COVID-19 (see [Section 6.4](#) for definition)
- Potential immune-mediated disorders ([Section 13.4](#))
- Anaphylaxis or severe hypersensitivity within 24 hours after study vaccine administration
- Myocarditis
- Pericarditis

Refer to [Section 6.1.1.3.1](#) for reporting AESIs.

### **6.1.1.2 Eliciting and Documenting Adverse Events**

Adverse events will be reported throughout the study. Nonserious AEs will be reported from the time of the administration of IP until 28 days after the administration of IP; SAEs will be reported from the time the participant signs the ICF until exit from the study.

If the investigator learns of any SAE, including a death, at any time after a participant has been discharged from the study, and he/she considers the event to be reasonably related to the IP, the investigator must notify PPD Pharmacovigilance within 24 hours of learning of the event ([Section 6.1.1.3.1](#)).

At every study visit, participants will be asked a standard nonleading question to elicit any medically related changes in their well-being.

In addition to participant observations, AEs identified from any study data (eg, laboratory values, physical examination findings) or identified from review of other documents (eg, participant eDiaries) that are relevant to participant safety will be documented on the AE page in the eCRF.

As described in [Section 6.1.1.1.1](#), participant eDiaries will be used to collect solicited AEs.

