#### Safety Assessments:

Safety will be assessed through the collection and evaluation of solicited AEs (for 7 days, the day of vaccination and 6 subsequent days); unsolicited AEs (for 28 days after study vaccination); and MAAEs, SAEs, and AESIs for the duration of the study. Local solicited AEs will include injection site pain, redness, and swelling and localized axillary, cervical or supraclavicular swelling or tenderness ipsilateral to the vaccination arm (lymphadenopathy). Systemic solicited AEs will include fever, fatigue, headache, chills, myalgia, and arthralgia. AESIs will include virologically confirmed COVID-19 disease, pIMDs, anaphylaxis or severe hypersensitivity within 24 hours after study vaccine administration, myocarditis, and pericarditis. Safety will also be assessed based on physical examinations, vital sign measurements, and clinical safety laboratory assessments (scheduled only at screening, Day 1, and Day 8).

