**Table 2-1 Study Objectives and Endpoints**

Primary Objectives	Primary Endpoints
To evaluate the safety and tolerability of CV0501 at each dose level	
 
Percentage of participants with each solicited local and systemic AE during 7 days after vaccination (ie, the day of study vaccination and 6 subsequent days, Days 1 through 7)
 
Percentage of participants with each abnormal clinical safety laboratory finding for 8 days after study vaccination
 
Percentage of participants with unsolicited AEs for 28 days after study vaccination
 
Percentage of participants with MAAEs, AESIs and SAEs from study vaccination through the end of the study (for 180 days after the study vaccine administration), each summarized separately
 

Secondary Objectives	Secondary Endpoints
To evaluate neutralizing Ab titers against SARS-CoV-2 WT, Omicron, and Delta variants following CV0501 booster vaccination in adult participants	
 
GMTs of neutralizing Ab against pseudovirus bearing S protein from SARS-CoV-2 WT, Omicron, and Delta variants at each collection timepoint
 
GMI from baseline of neutralizing Ab titers against pseudovirus bearing S protein from SARS-CoV-2 WT, Omicron, and Delta variants at each collection time point
 

To describe seroresponse to CV0501 based on neutralizing Ab titers against pseudoviruses bearing S protein from SARS-CoV-2 WT, Omicron, and Delta variants	
 
Seroresponse rate 28 days after the booster dose (Day 29), based on neutralizing Ab titers against pseudoviruses bearing S protein from SARS-CoV-2 WT, Omicron, and Delta variants at each collection timepoint, with seroresponse defined as postboost titers <math>\geq 4\times</math> preboost titers.
 

Tertiary Objectives	Tertiary Endpoints:
CCI	

GlaxoSmithKline Biologicals SA

CV0501 Vaccine

Protocol 218595 (CV2 SARS-COV2-012 BST) Amendment 2

26 Jul 2022

CCI

[figure not shown]

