f. A complete physical examination including height and weight will be performed at screening. Symptom-directed physical examinations will be performed as clinically indicated at subsequent visits.
- g. Vital sign measurements (temperature, pulse rate, oxygen saturation by pulse oximetry, respiration rate, and blood pressure) should be collected before and after study vaccination on D1. Vital sign measurements should be performed before any scheduled blood collection. Participants who are febrile (temperature  $\geq 38.0^{\circ}\text{C}$  or  $\geq 100.4^{\circ}\text{F}$ ) before study vaccination on D1 should be rescheduled for study vaccination within the relevant window period.
- h. Clinical safety laboratory testing will include hematology and serum chemistry. Screening laboratory tests may be repeated once for enrollment requirements. At unscheduled visits, clinical safety laboratory testing may be performed per investigator's discretion. Viral screening assays include HIV1/2 Antigen/Ab, hepatitis B surface antigen (HBsAg) and hepatitis C virus antibodies (HCV Abs). Testing for HCV RNA will be performed in participants who test positive for HCV Ab.
- i. An eDiary will be initiated for daily recording by the participant of solicited local and systemic adverse events.
- j. Solicited local and systemic AEs will be collected during the 7 days after study vaccination via eDiaries. Unsolicited AEs will be collected for 28 days after study vaccination. SAEs, MAAEs, and AESIs will be collected for the duration of the study.
- k. All suspected cases of COVID-19 in study participants will be diagnosed and clinically evaluated according to the definitions provided in [Section 6.1.2](#). Such participants may have unscheduled study site visits and nasopharyngeal RT-PCR testing for SARS-CoV-2. An unscheduled visit may be performed for participants reporting symptoms consistent with COVID-19. An initial visit should be scheduled upon report of symptom onset, preferably within 3 days of symptom onset. Alternatively, an investigator may utilize participant medical records from non-study care medical providers to verify whether a participant was infected with SARS-CoV-2. An additional unscheduled COVID-19 convalescent visit will be preferably conducted within the month after the participant is

GlaxoSmithKline Biologicals SA  
Protocol 218595 (CV2 SARS-CV0501-012 BST) Amendment 2

CV0501 Vaccine  
XX Jul 2022

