9.1.8 Medically Attended Adverse Events

Medically attended adverse events (MAAEs) is defined as an AE that results in a visit to a medical professional (eg, telephone call, physician's office visit, urgent care visit, emergency room visit or hospitalization). Scheduled study visits will not be considered medically attended visits. Medically attended adverse events related to study vaccination are to be reported from the time of first study vaccination until completion of the participant's last study-related procedure, which may include contact for safety follow-up.

The percentage of participants with MAAE onset date within day 1-180 will be provided by dose group and by grade.

All MAAEs and treatment-related MAAEs with onset date within day 1-28 and within day 1-180 will be presented in separate summary tables for each dose and age group and total by SOC and PT. All MAAEs will be presented in a data listing by age group, dose group and participant number.

MAAEs will be reported in both listings and summaries from the time participant signs the ICF until exit from study (up to day 180 after the study vaccine administration, day 1-180).

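### Protocol 6.1.1.2 ends nonserious AE reporting at 28 days and exempts only SAEs, contradicting the study-end primary endpoint and leaving late nonserious MAAEs exposed

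*Protocol*

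**What the plan says.** - **Protocol 6.1.1.2** opens with "Adverse events will be reported throughout the study". The next sentence divides events by seriousness: "Nonserious AEs will be reported from the time of the administration of IP until 28 days after the administration of IP", and then "SAEs will be reported from the time the participant signs the ICF until exit from the study". It makes no exception for MAAEs or AESIs.
- **Protocol Table 2-1** has a primary endpoint for the percentage of participants with "MAAEs, AESIs and SAEs from study vaccination through the end of the study". The period is put at 180 days, and each event type is summarized separately.
- **Protocol synopsis, Safety Assessments**, provides for collecting "MAAEs, SAEs, and AESIs for the duration of the study".
- **Protocol Schedule of Events, footnote j**, applies the 28-day limit to unsolicited AEs and continues: "SAEs, MAAEs, and AESIs will be collected for the duration of the study".
- **Protocol 6.1.1.1.1** defines an MAAE as an AE that leads to contact with a medical professional, telemedicine and office visits included. An MAAE therefore need not be serious. The definition sets no reporting window.
- **SAP Section 4** analyses MAAEs, AESIs and SAEs over Day 1 to 180.
- **SAP 9.1.8** contains the sentence beginning "Medically attended adverse events related to study vaccination are to be reported from the time of first study vaccination". It then calls for separate tables of all MAAEs and of related MAAEs, and for a listing of all of them.

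**The concern.** Section 6.1.1.2 is where a site looks to learn when to stop reporting an event. It uses one criterion, seriousness, and stops every nonserious event at 28 days. The primary endpoint uses a different criterion, event type, and follows MAAEs and AESIs to study end. A nonserious MAAE that starts on, say, Day 60 counts toward the endpoint but falls outside the reporting rule.

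Sites following 6.1.1.2 would undercount a primary safety endpoint, while sites following footnote j would not. The result would mix two ascertainment windows within the same table. An event that was never entered cannot be restored by any analysis method, so this has to be settled in the reporting instructions.

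**Working it through.** **Step 1. The windows side by side.**

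| Source | Nonserious MAAE | Nonserious AESI | SAE |
|---|---|---|---|
| Protocol 6.1.1.2 | to 28 days | to 28 days | to study exit |
| Protocol Table 2-1 | 180 days | 180 days | 180 days |
| Protocol synopsis; footnote j | study duration | study duration | study duration |
| SAP Section 4 | Day 1–180 | Day 1–180 | Day 1–180 |

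The first row disagrees with the others for nonserious MAAEs and AESIs, and agrees in substance for SAEs.

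**Step 2. Which events are actually exposed.** An event is exposed only if it is nonserious, starts after 28 days, and has no other rule that brings it in.

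| Event | Other rule | Exposed? |
|---|---|---|
| Myocarditis, pericarditis | Always SAEs (Protocol 6.1.1.1.2) | No |
| Anaphylaxis or severe hypersensitivity AESI | Limited to the first 24 hours (6.1.1.1.4) | No, inside 28 days |
| Nonserious confirmed COVID-19 | Monitored to Day 181 (Section 3); reported as an AESI (6.1.2); 24-hour reporting with no end date (6.1.1.3.1); SAP 8.1.1 tabulates nonserious cases to study end | Largely protected |
| Nonserious potential immune-mediated disease | Expedited report whether serious or not (Appendix 4); 24-hour AESI reporting | Largely protected |
| Nonserious MAAE that is not an AESI | None in Section 6 | **Yes** |

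Section 6.1.1.3.1 covers SAEs and AESIs only. For a nonserious MAAE, the specific stop date given in Section 6 is the one in 6.1.1.2.

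**Step 3. Calendar time.** The endpoint window is 180 days (Table 2-1) and the reporting window is 28 days (6.1.1.2). The difference is 180 − 28 = 152 days, and 152/180 = 84.4%.

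**Step 4. What this could do to the endpoint (illustration only).** The documents give no MAAE incidence, so a range is assumed.

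The plan's own detection probabilities (Protocol 7.2) reproduce first, using P(at least 1) = 1 − (1 − p)^n:
- n = 30, p = 5%: 78.54% (stated 78.5%)
- n = 30, p = 10%: 95.76% (stated 95.8%)
- n = 15, p = 10%: 79.41% (stated 79.4%)

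Now let p180 be the true 180-day incidence of nonserious MAAEs. Assume a constant hazard, and assume that every site applies the 28-day rule literally. Then p28 = 1 − (1 − p180)^(28/180). For p180 = 10%, p28 = 1 − 0.90^0.1556 = 1.6%, and for n = 30 the chance of seeing at least one event is 1 − 0.90^(30 × 28/180) = 1 − 0.90^4.667 = 38.8%.

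| Assumed p180 | Seen by 28 days | P(≥1), n = 30, full window | P(≥1), n = 30, 28 days |
|---|---|---|---|
| 5% | 0.8% | 78.5% | 21.3% |
| 10% | 1.6% | 95.8% | 38.8% |
| 20% | 3.4% | 99.9% | 64.7% |
| 40% | 7.6% | >99.9% | 90.8% |

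These are worst-case figures. Visits that cluster soon after vaccination, or sites that follow footnote j, would shrink the loss.

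**The case against.** The strongest reply is that the protocol, read as a whole, makes its intent plain. The synopsis, Table 2-1 and footnote j agree with one another. Section 6.1.1.2 itself opens by saying that AEs are reported throughout the study. It also has participants asked about their health at every visit, which includes Days 91 and 181. Sections 6.1.1.1.1 and 6.1.1.3 speak generally of reporting and recording all AEs seen during the study, and Section 6 sends sites to the Schedule of Events. On this reading, 28 days was meant for ordinary unsolicited AEs.

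That argument stands as to intent, and it makes the repair uncontroversial. It does not remove the contradiction. The general statements give no stop date for a nonserious event; the sentence in 6.1.1.2 does, and it narrows the sentence before it. Asking about health at Day 91 does not tell the site whether to enter a nonserious answer.

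Two stronger readings are tempting, and the documents do not support them:
- **That nonserious AESIs would be lost as well.** Section 6.1.1.1.4 defines AESIs as serious or nonserious and refers the site to 6.1.1.3.1, which has no seriousness condition and no end date. COVID-19 and potential immune-mediated diseases have further rules of their own. The missing exemption for AESIs is a wording fault with little practical exposure.
- **That the SAP restricts the MAAE endpoint to vaccine-related events.** One sentence in 9.1.8 has that phrase, but the same section tabulates and lists all MAAEs. The phrase is stray wording and does not set a competing endpoint.

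The public documents also limit what can be inferred. The schedule row that carries footnote j is not visible, and the eCRF and its completion guidance are not supplied. How sites are in practice told to enter late MAAEs cannot be judged here.

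**Conclusion.** The point holds as an internal inconsistency. Section 6.1.1.2 conflicts with the primary endpoint, the synopsis and footnote j because it exempts only SAEs from the 28-day limit. The practical exposure is mainly nonserious MAAEs with onset after 28 days.

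Applied literally, the rule leaves 152 of 180 days (84% of calendar time) without nonserious MAAE reporting. A reader might take the 84% as the share of events lost. It is not: it counts days, and it matters only where a site or the eCRF follows 6.1.1.2 over footnote j. The number of events at risk is unknown, and the table of assumed incidences shows only how large the effect could be under a constant hazard and universal literal application. Earlier nonserious MAAEs and all SAEs stay in the endpoint. No sample-size figure or analysis method changes.

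It should be corrected because a primary safety endpoint depends on it, the loss would be permanent, and the intended window is already stated elsewhere in the protocol.

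**What to change.** Reconcile Protocol 6.1.1.2 with Table 2-1 and footnote j. State that the 28-day limit applies to unsolicited nonserious AEs that are neither MAAEs nor AESIs, and that MAAEs and AESIs are reported from vaccination to study exit regardless of seriousness. Check that the eCRF completion guidance accepts a nonserious MAAE with onset after 28 days.

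As a minor clean-up, delete the words limiting MAAEs to those related to study vaccination from the reporting sentence in SAP 9.1.8, since that section already summarizes and lists all MAAEs.

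The cost is one clause in the protocol, communicated to sites, and one phrase in the SAP. No data collection is added beyond what footnote j already requires.

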### **6.1.1.2.1 Assessment of Intensity**

The intensity, or severity, of an AE refers to the extent to which an AE affects the participant's daily activities.

Solicited AEs will be graded in intensity by the participant. The investigator will assess the maximum intensity that occurred over the duration of the event for all unsolicited AEs, including SAEs, recorded during the study. The assessment will be based on the investigator's clinical judgment.

The intensity of the following solicited events will be assessed as described in [Table 6-1](#).

**Table 6-1** **Intensity Scales for Solicited Symptoms**

Event	Intensity Grade	Parameter
Pain at administration site	0	None
	1	Mild: Any pain neither interfering with nor preventing normal everyday activities
	2	Moderate: Painful when limb is moved and interferes with everyday activities
	3	Severe: Significant pain at rest. Prevents normal everyday activities
Redness at administration site	0	<2.5 cm
	1	2.5 – 5 cm
	2	5.1 – 10 cm
	3	>10 cm
Swelling at administration site	0	<2.5 cm
	1	2.5 – 5 cm and does not interfere with activity
	2	5.1 – 10 cm or interferes with activity
	3	>10 cm or prevents daily activity
Lymphadenopathy a	0	None
	1	Mild: No interference with activity
	2	Moderate: Some interference with daily activity or requires repeated use of non-narcotic pain reliever
	3	Severe: Prevents daily activity or requires use of narcotic pain reliever
Temperature b	0	<38.0°C or <100.4°F
	1	38.0 – 38.4°C or 100.4 – 101.1°F
	2	38.5 – 38.9°C or 101.2 – 102.0°F
	3	>38.9°C or >102.0°F
Headache	0	Normal
	1	Mild: Headache that is easily tolerated
	2	Moderate: Headache that interferes with normal activity
	3	Severe: Headache that prevents normal activity
Fatigue	0	Normal
	1	Mild: Fatigue that is easily tolerated
	2	Moderate: Fatigue that interferes with normal activity
	3	Severe: Fatigue that prevents normal activity
Myalgia	0	Normal
	1	Mild: No interference with daily activity
	2	Moderate: Interferes with daily activity
	3	Severe: Prevents daily activity
Arthralgia	0	Normal
	1	Mild: No interference with daily activity
	2	Moderate: Interferes with daily activity
	3	Severe: Prevents daily activity
Chills	0	None
	1	Mild sensation of cold; shivering; chattering of teeth
	2	Moderate tremor of the entire body; narcotics indicated
	3	Severe or prolonged, not responsive to narcotics

a. Defined as localized axillary, cervical or supraclavicular swelling or tenderness ipsilateral to the vaccination arm.

b. Refer to [Section 6.1.4](#) for the definition of fever.

The intensity of AEs will be assigned to one of the following categories:

- Grade 1 (Mild): An AE that is easily tolerated by the participant, causing minimal discomfort, and not interfering with everyday activities.
- Grade 2 (Moderate): An AE that is sufficiently discomforting to interfere with normal everyday activities.
- Grade 3 (Severe): An AE that prevents normal, everyday activities. In adults, such an AE would, for example, prevent attendance at work and would necessitate the administration of corrective therapy.

An AE that is assessed as Grade 3 (severe) should not be confused with an SAE. Grade 3 is a category used for rating the intensity of an event; and both AEs and SAEs can be assessed as Grade 3. An event is defined as “serious” when it meets the definition of an SAE ([Section 6.1.1.1.2](#)).

Refer to [Section 6.1.2](#) for grading of laboratory-associated AEs.

Changes in the severity of an AE should be documented to allow an assessment of the duration of the event at each level of intensity. Adverse events characterized as intermittent do not require documentation of onset and duration of each episode.

